#### 8.7.6.2. ENDOMETRIAL ASSESSMENT: TISSUE COLLECTION AND ULTRASOUND

A Transvaginal Ultrasound or Transabdominal (Pelvic) Ultrasound (TVUS) will be performed at CCI/Screening and CCI / End of TRC3 to assess endometrial thickness and if there is a clinically significant changes in endometrial thickness and histology. Endometrial biopsies are optional for all participants except in the case of abnormal vaginal bleeding (at discretion of the Investigator).

- The following variables will be assessed.
  - Endometrial thickness (mm)
  - Proportion of participants with clinically significant changes from CCI
    - i) In endometrial thickness as assessed by transvaginal ultrasound and
    - ii) Histological findings as assessed by optional endometriosis biopsy (using an endometrial suction curette Pipelle®)

The endometrial thickness will be summarized by treatment group and visit using descriptive statistics of observed data and change from baseline values. Similar analysis for the primary efficacy variable described in Section 8.3.7 using ANCOVA will be performed for the change from baseline to CCI/EOT in endometrial thickness.

The number and percentage of participants with clinically significant changes in endometrial thickness and histology from CCI will be summarized.

#### 8.7.6.3. PREGNANCY TEST AND LACTATION

Urine pregnancy test (human chorionic gonadotropin) and/or serum  $\beta$ -hCG pregnancy tests are performed throughout the study in female subjects of childbearing potential.

Pregnancy outcomes and lactation information collected on eCRF Pregnancy/Lactation page will be presented in a listing.

#### 8.7.6.4. COLUMBIA SUICIDE SEVERITY RATING SCALE (C-SSRS)

A positive C-SSRS response is defined when there is a positive answer ("Yes"), at any time during treatment, to any one of the questions (suicidal ideation / behavior) on the C-SSRS questionnaire.

Positive C-SSRS responses observed at any post-baseline assessment will be summarized by treatment group for the SAF using descriptive statistics for categories of Suicidal Ideation, Suicidal Behavior and Self-Injurious Behavior without Suicidal Intent, as well as for the 11 individual questions associated with each category.

#### 8.7.6.5. PHYSICAL, GYNECOLOGICAL AND BREAST EXAMINATION

Physical, gynecological and breast examination findings after ICF are recorded in the eCRF AE page and will be presented in the AE listing. A listing of gynecological examination assessments in participants who had abnormal PAP smear results will be provided.

#### 8.7.6.6. BONE BIOMARKER

The following bone biomarker measurements will be reported for this study:

CC [REDACTED]  
CC [REDACTED]

The following summaries will be provided for bone biomarker data:

- Observed and change from baseline (CC) to end of treatment (CC)

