In this Phase 2a/b 4-arm PoC, dose-range study, treatment over CCI is intended to assess the effect of treatment with OG-6219 on efficacy, safety, and tolerability over 6 menstrual cycles.

While a previous study in cynomolgus monkeys exposed to OG-6219 for a total of CCI did not find any statistically significant changes in the mean CCI. An increase CCI in this Phase 2a/b study, if any, is expected to be fully and quickly reversible.

CCI

Also, no macroscopic or microscopic effect on bone tissue was observed in the CCI toxicology studies in rat and cynomolgus monkeys. However, no clinical experience on the effect of OG-6219 on systemic estrogen levels with longer exposure is available.

CCI

Effects on coagulation and lipid parameters as well as cardiovascular function will be monitored by serum chemistry, vital signs, and ECGs.

Participants will need to stop using any previous hormonal treatment for endometriosis as well as oral and other contraceptive treatment to enable assessment of the effect of HSD17 β 1 inhibition by OG-6219 on ERP, and menstrual regularity of the endometrium (refer to the [Table 2](#) and [Appendix 7](#)).

Embryo-fetal survival and development during the organogenesis phase of pregnancy was studied in pregnant rats and cynomolgus monkeys and no effect of OG-6219 treatment was found at the respective highest doses tested. However, as the effect of OG-6219 on fertility and early embryonic development and pre- and post-natal development has not been studied at this time, the risk of reproductive toxicity cannot be considered fully characterized. Therefore, necessary precautions to prevent pregnancy will be taken in this study. Participants will be informed about the risks to become pregnant and should not plan to become pregnant over the course of the study; only participants who are abstinent, or who are willing to reliably use an acceptable effective method for contraception as described in detail in the protocol (refer to the [Appendix 5](#)) and informed consent, or in whom safe contraception is achieved by a permanent method, will be eligible. A negative serum β -human chorionic gonadotropin (β -hCG) test prior to randomization and start of the treatment will be required, and monthly urinary pregnancy tests will be performed during the study implementation. Any pregnancy

will trigger withdrawal from study treatment, participant to expedited reporting and outcome of the pregnancy will be followed.

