9.4.3 Secondary Endpoint Analysis

Secondary endpoints assessing change in continuous endpoints over time (either measurements within the cycle or at an individual visit) will use longitudinal models as described for the primary endpoint and/or ANCOVA models. Changes from SC to SFC will be compared using ANCOVA models in the SFAS. Select longitudinal models which focus on TRC1 and TRC2 may exclude TRC3 from the model. An unstructured error structure will be assumed for all longitudinal models. If nonconvergence is encountered, CS and AR (1) error structures will be considered.

Definitions corresponding to the incidence of clinically significant values will be provided in the SAP.

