5. To evaluate the change in the PGI-S Score at different time points	
 
Change in PGI-S Score from C to Phone Contact CCI
 

6. To evaluate the change in the PGI-C Score in different time points	
 
Percentage of participants with any improvement on the PGI-C at TRC1, TRC2, and TRC3
 

7. To evaluate the change in the EHP-30 domains (CCI ) from BC to TRC3	
 
Change from BC to TRC3 in the EHP-30 Domain Scores
 

Secondary Safety Endpoints	
8. To assess the incidence of clinically significant b changes from V1 to C in bone biomarkers: 	
 
Mean change from V1 to C in bone biomarker levels
 

9. To assess the incidence of any clinically significant b changes in laboratory parameters from V1 to CC 	
 
Proportion of participants with clinical parameters of significance from V1 to CCI
 

10. To assess vaginal bleeding pattern over the 3 menstrual cycles (TRC1, TRC2, and TRC3) as captured in the eDiary	
 
Mean change from BC to TRC1, TRC2, TRC3 in the number of days on period and number of days with irregular vaginal bleeding/spotting
 

11. To assess any potential change in the ECG parameters at CCI	
 
ECG parameter changes at CCI
 

Secondary PD / PK Endpoints	
12. To assess the change from CCI in serum hormone c concentrations	
 
Mean change from CCI in serum hormone levels
 

13. To assess any difference in serum hormone c concentrations at C between active treatment versus placebo	
 
Serum hormone levels at V5 comparing Group A (CCI BID), B (CCI BID), C (CCI BID) with Group D (Placebo)
 

Version Date: 09JUN2025

- Treatment Cycle 1 is the period between the first day of menses associated with treatment start (C) to the day prior to the first day of next menses, regardless of number of days.
- Treatment Cycle 2 is the period between the first day of second menses after end of BC to the day prior to first day of next menses, regardless of number of days.
- Treatment Cycle 3 or EOT is the period between the first day of third menses after end of BC to either end CCI on study treatment, whichever occurs first.

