#### 4.3. Sample Size

Approximately 760 pre-menopausal females aged 18 to 49 years old (inclusive), who have been surgically diagnosed with endometriosis within the last 4 months to 10 years prior to V1, will be screened to achieve 380 randomly assigned to the study treatment (95 participants in each group). A total of 380 participants will provide 84% power to detect a difference of 1 point between an OG-6219 dose group and Placebo in change from baseline to TRC3 of mean OPP, assuming a common SD of 2.2. This power calculation is based on a 2-sided test with Type I error of 0.05 and a dropout rate of 10%.

A minimum subset of 10 participants per group (~10%) will be enrolled for optional intensive PK sampling for the entire duration of the study.

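### SAP 8.7.6.6 keeps the bone biomarkers descriptive although Protocol 9.4.3 plans modelled comparisons and an incidence definition, and SAP section 10 declares no change

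*SAP*

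**What the plan says.** - **SAP 8.7.6.6** lists the markers (names blacked out) and gives a single summary: "Observed and change from baseline (CC) to end of treatment (CC".
- **Objective 8** in Protocol Table 1 and SAP Table 1 is about the incidence of clinically significant "changes from V1 to C in bone biomarkers". The endpoint printed beside it is a mean change.
- **Protocol 9.4.3** assigns longitudinal models, ANCOVA or both to secondary endpoints that measure change on a continuous scale, whether over a cycle or at one visit. It adds: "Definitions corresponding to the incidence of clinically significant values will be provided in the SAP".
- **Protocol 9.4.1** says every model compares one dose arm with placebo, and that summary statistics are shown by treatment group.
- **SAP 8.7.6.2**, on the endometrium, goes further than 8.7.6.6: a model "using ANCOVA will be performed for the change from baseline to CCI/EOT in endometrial thickness", plus the number and percentage of women with a clinically significant change. **SAP 8.6.3** gives the serum hormones a log-scale ANCOVA against placebo with 95% CIs.
- **SAP section 10** states that no protocol-planned analysis was changed; it notes only that the estimand was added.

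**The concern.** The protocol makes two commitments that appear to reach the bone biomarkers, a model and a definition of significant change, and SAP 8.7.6.6 carries out neither. Section 9.4.3 is not limited to efficacy. Among the objectives that can be read, only safety objectives 8 and 9 speak of an incidence of clinically significant change, so its sentence on definitions points at them.

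The protocol's rationale names effect on bone among the things safety is meant to cover, and section 2.3.3 promises close monitoring of it. If the SAP stands, any comparison with placebo on bone turnover would have to be chosen after unblinding. A mean can also conceal a few women with large changes, which an incidence is suited to show.

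**Working it through.** **1. The plan's only relevant figure.** SAP 4.3 states: "A total of 380 participants will provide 84% power to detect a difference of 1 point", with 95 women per group, SD 2.2, two-sided alpha 0.05 and 10% dropout. Evaluable per arm: 95 × 0.90 = 85.5, taken as 85.

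Standard error = 2.2 × √(2/85) = 0.337. Then 1/0.337 = 2.963, and Φ(2.963 − 1.960) = 0.842. The 84% reproduces. It concerns overall pelvic pain; the documents give no SD, power or threshold for the bone biomarkers.

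**2. What the text requires and what it delivers for bone.**

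| Item | Protocol | SAP 8.7.6.6 |
|---|---|---|
| Mean change (paired endpoint) | Table 1 | Delivered, descriptively |
| Longitudinal model or ANCOVA | 9.4.3 | None |
| Dose versus placebo with CI | 9.4.1 and 9.4.2, through 9.4.3 | None |
| Definition for incidence | 9.4.3, left to the SAP | Generic table footnote only |
| Count of women affected | Objective 8 wording | None |
| Departure declared in SAP section 10 | – | None |

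**3. What baseline adjustment is worth.** Assume equal SD σ at V1 and end of treatment, and correlation rho between the two.

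- Variance of a raw change: 2σ²(1 − rho).
- ANCOVA residual variance: σ²(1 − rho²).
- Ratio: (1 − rho²) / [2(1 − rho)] = (1 + rho)/2, a reduction of (1 − rho)/2.

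The 95% CI half-width for one dose against placebo is 1.96 × √(2 × variance/85). Since rho is not in the documents, a range is shown, in units of σ:

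| Assumed rho | Raw change | ANCOVA | Variance ratio |
|---|---|---|---|
| 0.3 | 0.356 | 0.287 | 0.65 |
| 0.5 | 0.301 | 0.260 | 0.75 |
| 0.7 | 0.233 | 0.215 | 0.85 |
| 0.8 | 0.190 | 0.180 | 0.90 |

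**4. What an incidence comparison could show.** With 85 per arm and rates assumed only for illustration, power is 0.59 for 5% against 15%, 0.85 for 5% against 20%, and 0.45 for 10% against 20%. An incidence table would therefore be better read as estimates than as tests.

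**The case against.** The strongest reply is that the SAP does deliver the endpoint paired with objective 8. The clash between an incidence objective and a mean-change endpoint starts in the protocol's own table. That stands. A reader might infer that objective 8 goes wholly unanswered; the documents do not support this.

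Nor do they support the inference that the trial could neither show nor exclude a bone signal. SAP 8.1.1 provides n, mean and SD of change, and Protocol 9.4.1 has them by treatment group, so anyone can compute an unadjusted difference and interval.

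There is also a partial route to incidence. A footnote to the objectives table defines clinical significance in general terms, and Protocol 8.3.7 has clinically significant laboratory changes recorded as adverse events. But that rests on investigator judgement, and the adverse event tables do not isolate bone markers. The two wordings also differ: the footnote asks that care may be altered, 8.3.7 that it is. The normal-range shift tables in SAP 8.7.2 might extend to bone markers, but the text does not say so.

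A reader might conclude that bone has been singled out for weak treatment. It has not: laboratory values, ECG, vital signs and bleeding are also descriptive, and the hormones are compared with placebo because objectives 13 and 14 ask for it, which objective 8 does not. Nor is this sentence in Protocol 2.3.1 about bone: "However, no clinical experience on the effect of OG-6219 on systemic estrogen levels with longer exposure is available". It concerns estrogen, and the sentence before it reports no effect on bone tissue in the animal studies.

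Finally, redaction limits what can be said. The text between Protocol 9.4.7.2 and 9.4.7.4 is blacked out, as is most of 8.8, so it cannot be confirmed that these markers are the only bone measure.

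**Conclusion.** The concern holds as a protocol–SAP reconciliation point of modest size. Protocol 9.4.3 calls for a model and a definition; SAP 8.7.6.6 has neither, and SAP section 10 says nothing changed. What is lost is a pre-specified, baseline-adjusted contrast of each dose with placebo, and the incidence named in objective 8.

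The precision at stake is small if rho is high: 10% of the variance at 0.8 and 15% at 0.7, rising to 35% at 0.3. These figures assume rho, equal SDs at both times, and that the 10% dropout set for the pain endpoint applies here. Pre-specification is the stronger reason to act. The case also rests on reading 9.4.3 as covering safety endpoints. Its wording supports that, but the redacted safety text could qualify it.

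**What to change.** In SAP 8.7.6.6 add, for each biomarker, an ANCOVA of the change from V1 to end of treatment with treatment and the baseline value as terms. Report each dose against placebo with a 95% CI. If the markers are skewed, use the log scale and back-transformation of SAP 8.6.3; settle the scale before unblinding.

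Reconcile objective 8 with its endpoint in one of two ways:

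- tabulate n (%) by arm of women with a clinically significant change, under a definition that the sponsor sets and fixes in the SAP before unblinding; or
- record in SAP section 10 that no incidence will be tabulated, and why.

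If the sponsor holds that 9.4.3 was never meant for safety endpoints, section 10 is the place to say that too.

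The cost is one model per biomarker and at most one small table, on data already planned for collection; sample size, power and alpha are unaffected. The drawback is three more nominal, unadjusted comparisons per biomarker, which should be presented as estimates.

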## 9. PHARMACOKINETIC ANALYSIS

Plasma concentrations of OG-6219 and FOR-1011 will be summarized for the PK analysis set and for the PK analysis set for NCA using descriptive statistics.

Calculation of pharmacokinetic parameters will be performed by IQVIA and the methods of calculation are described in a separate document.

Calculated pharmacokinetic parameters for OG-6219 and FOR-1011 will be summarized for the PK analysis set for NCA using descriptive statistics. In addition to the standard descriptive statistics described in section 8.1.1, geometric mean and coefficient of variation

(CV) will be included for all PK parameters except  $t_{\max}$  and  $t_{\text{last}}$ .

Individual and mean plasma concentration data will be illustrated using both a linear and a logarithmic concentration scale.

## 10. CHANGES TO PROTOCOL-PLANNED ANALYSES

There were no changes to the analyses planned in the study protocol.

The study protocol did not include a description of the estimand. This has now been included in the SAP.

